12.2 Group B Treatment cohort primary endpoint

- Resolution of SARS-CoV-2 defined as non-detection of SARS-CoV-2 RNA in two

respiratory samples by or on day 14

13. Statistical Considerations

13.1 Sample Size and Power Considerations

The planned sample size for the trial is 164 participants enrolled and randomized in a 1:1 ratio to lambda interferon-1a versus placebo injection. This sample size is based on the expectation that approximately 32.5% of participants who are enrolled have evidence of SARS-CoV-2 at study entry (an intermediate value consistent with the 25 – 40% infection range that we expect for the study outcome in the placebo group), thus around 110 will be will have no evidence of SARS-CoV-2 infection (Prevention Cohort) at enrollment and around 54 participants will have evidence of SARS-CoV-2 infection (Treatment Cohort). The Treatment Cohort represents an exploratory pilot study to provide estimates of antiviral efficacy for early COVID-19. Power estimates for the study are based on the Prevention Cohort and incorporate the following assumptions (multiple credible scenarios are presented):

The primary analysis for the efficacy/prevention of infection with SARS-CoV-2 in the Lambda interferon-1a and the placebo groups using proportional odds model and a two-sided Type I error rate (α) of 0.05. Since participants in both the Prevention and Treatment Cohorts will be dosed after entry, we anticipate that few, if any participants will not start treatment and be excluded from the primary analysis. Further, given the nature of COVID-19, we anticipate low rates of loss to follow-up before the primary endpoint (Day 14). We expect the incidence of new COVID-19 in the placebo group to be between 25% to 40%, thus we will perform calculation for these edge-case scenarios. In addition, we will be offering enrollment to all adults in a household (~2 per household), our analysis sample will be clustered-correlated by household. However, there is no preliminary or published data to model within-cluster correlation. Thus we are modeling scenarios where the effective sample size is as high as 110 individuals, or as low as the number of households of 55. In all scenarios, we are expecting that the cumulative infection fraction for the lambda interferon will be 5%.

Cumulative Infection Percentage in Placebo	Effective sample size	
	N= 110 individuals	N = 55 family clusters
25%	80.1%	36.1%
40%	99.6%	84.0%

We note that we have 80% or greater power (and Type II error rate beta of 0.2 or smaller) in a large range of scenarios.

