POPULATION Household contacts of patients confirmed to have COVID-19 based on SARS-CoV-2 RT-PCR. Consented participants will subsequently enter the treatment or prevention cohorts based on the presence or absence of SARS-CoV-2 on the nasopharyngeal sample obtained at study entry.

Group A: Non-hospitalized, household contacts of individuals with confirmed COVID-19 infection who test RT-PCR negative for SARS-CoV-2 infection at study entry (Prevention cohort)

Group B: Non-hospitalized, household contacts of individuals with confirmed COVID-19 infection who test RT-PCR positive for SARS-CoV-2 at study entry (Treatment cohort).

All participants ≥ 18 years of age who are household contacts of individuals with confirmed COVID-19 infection (within 7 days of diagnosis) without self-report of symptoms of acute respiratory illness (fever, cough or shortness of breath).

At the time of enrollment, the SARS-CoV-2 infection status of the participant will not be known and their inclusion in Group A (Prevention cohort) or Group B (Treatment cohort) will be based on the results of upper respiratory tract sampling at study entry. Participants without detection of SARS-CoV-2 RNA at the time of screening/enrollment will constitute Group A (Prevention cohort) whereas as those with detection of SARS-CoV-2 RNA will constitute Group B (Treatment cohort).

At enrollment into Step 1, all participants in both Group A and B will be non-hospitalized and have a normal blood oxygen saturation by pulse oximetry ($\geq 95\%$) on room air and a respiratory rate of fewer than 25 breaths/minute.

REGIMEN

Enrollment occurs in two Steps. After confirming eligibility, participants are enrolled into Step 1.

Prior to knowledge of infection status, participants will be randomized 1:1 to treatment with peginterferon lambda-1a (Lambda) 180 micrograms by subcutaneous injection one dose (Active Arm) or placebo by subcutaneous injection (Placebo Arm).

Duration of treatment is one week with an additional three week observation period.

Based on the results of SARS-CoV-2 RT PCR testing of upper respiratory tract samples at the time of enrollment into Step 1, persons who test RT-PCR negative at Day 0 will constitute group A.

Participants who test RT-PCR positive for SARS-CoV-2 at entry make up Group B, the treatment cohort.

Group A Prevention Cohort	Day 0	Ratio
Active	Active	1
Placebo	Placebo	1

Group B Treatment Cohort	Day 0	Ratio
Active	Active	1
Placebo	Placebo	1

PRIMARY OUTCOMES

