8.9. Randomization

Randomization will take place on day 0 after screening activities have been performed and the Investigator or designee has determined that the participant is eligible. Day 0 laboratory tests including blood SARS-CoV-2 RT-PCR results are not part of the eligibility criteria and participants will be randomized without this information. Randomization will be built into the study REDCap database. It will not be known at entry/screening whether participants are part of Group A or Group B since their COVID-19 infection status will not be known until entry/screening specimens are processed. All participants will be randomized in a 1:1 ratio to receive Lambda/Lambda (Arm 1) or Placebo/Placebo (Arm 2). Participants who are not eligible for enrollment into Step 2 (will be removed from protocol therapy Single dose of Lambda or placebo) respectively.

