13.2 Statistical Analysis

13.2.1 Analyses will include all randomized participants Our primary analysis for both the prevention and treatment cohorts (outcomes of non-infection and resolution, respectively) will be mixed model logistic regression correcting for within-household correlation as a random effect. In addition to the placebo cumulative infectivity and odds ratios, we will express the overall

cumulative incidence of infection and the difference between lambda interferon vs. placebo using nonlinear combination (i.e., inverse logit of the placebo and active treatment groups and the difference of these after the inverse logit transformation). Statistical inference will use a two-sided Type 1 error rate of 0.05 and 95% confidence intervals.

For the exploratory treatment cohort, we will similarly examine clearance of infection.

In addition, we will perform survival analysis for time to infection in the prevention cohort and time to infection clearance in the treatment cohort, modeling within cluster correlation of hazard as a random effect (frailty).

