14.1 Monitoring Plan

All AE and SAE will be reviewed by the protocol team twice monthly, or more if needed.

The Principal Investigator will be responsible for safety oversight of the clinical study.

A data safety monitoring board (DSMB), composed of independent experts without conflict of interests will be established. The Board will review the study before initiation and after 50% of planned enrolled participants have reached the primary endpoint. The Board will review study data to evaluate the safety, efficacy, study progress, and conduct of the study.

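### The section 13.1 power table is fixed-sample Fisher-type power: it matches neither the named analyses nor the section 14.4 futility stop, which takes the 25%/110 cell from 80.1% to about 76–79%

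*Combined protocol and SAP*

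**What the plan says.** Section 13.1 describes the primary analysis as "using proportional odds model and a two-sided Type I error rate" of 0.05. It assumes 5% cumulative infection on lambda and 25% or 40% on placebo. Because all adults in a household may enrol (about two each) and no correlation data exist, it brackets the answer: "the effective sample size is as high as 110 individuals, or as low as the number of households of 55". The table gives 80.1% (25% placebo) and 99.6% (40%) for N = 110, and 36.1% and 84.0% for 55 clusters. The text then says "We note that we have 80% or greater power" across many scenarios.

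Section 13.2.1 plans a different primary analysis, "mixed model logistic regression correcting for within-household correlation as a random effect". Section 8.9 words allocation by participant: "All participants will be randomized in a 1:1 ratio to receive Lambda/Lambda (Arm 1) or Placebo/Placebo (Arm 2"; the Regimen part of the Synopsis reads the same way. No section says that households are allocated as units.

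Section 14.1 has the board review the data "after 50% of planned enrolled participants have reached the primary endpoint". Section 14.4 adds O'Brien-Fleming p-value limits of 0.0054 (interim) and 0.0492 (final), and a futility stop when conditional power, with the trend so far continuing, is below 10%. Section 13.1 mentions none of these rules.

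**The concern.** A power table should describe the design that will be run. Here the test behind the table is not named, the text names two other analyses, and the stopping rules are absent. The printed margin in the 25%/110 cell is 0.1 point, so even a small omitted loss takes it under 80%. At 25% placebo incidence no other cell reaches 80%. The effective sample size of 55 also belongs to a design in which whole households share an arm, which is not how allocation is worded. A reader therefore cannot tell what power the planned trial has, or in which direction the printed figures are off.

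**Working it through.** **Inputs.** From 13.1: lambda rate 5%, placebo rate 25% or 40%, two-sided α = 0.05, N = 110 or 55. From 14.1 and 14.4: one look at half the sample, limits 0.0054 and 0.0492, futility at conditional power below 10% under the current trend. Assumptions: no missing outcomes; the interim splits listed below.

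**1. Reproducing the table.** Power = Σ Bin(x; n, p_placebo) · Bin(y; n, 0.05) over all (x, y) with Fisher p ≤ 0.05.
- n = 55 per arm: 80.12% and 99.57%.
- n = 27 per arm: 36.11% and 84.01%.

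All four cells match to 0.1 point. Exact enumeration of the Yates-corrected chi-square gives the same values. Other methods do not match; for 25%/110, the pooled normal formula gives 84.6%, Pearson 87.3% and the likelihood ratio 88.8%. The 55 column needs 27 per arm; a 28/27 split gives 39.6% and 86.6%.

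**2. Adding the 14.4 rules to the same test.** Two versions of current-trend conditional power were used.
- *Observed rates*: enumerate the second half at the interim rates and stop if the chance of final p < 0.0492 is below 10%.
- *Interim z*: the final critical value is 1.967. At half information, conditional power = Φ[(z√0.5 + 0.5·z/√0.5 − 1.967)/√0.5] = Φ(2z − 2.782). This equals 10% at 2z − 2.782 = −1.282, so z = 0.75.

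Ranges are over interim splits 28/27, 27/28, 27/27 and 28/28 (N = 110), and 14/13, 13/14, 13/13 and 14/14 (27 per arm):

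| Cell | Printed | Efficacy limits only | Futility obeyed, observed rates | Futility obeyed, z < 0.75 |
|---|---|---|---|---|
| 25% / 110 | 80.1 | 80.2–80.4 | 76.1–77.0 | 78.6–79.0 |
| 40% / 110 | 99.6 | 99.6 | 99.1–99.2 | 99.3–99.4 |
| 25% / 55 | 36.1 | 36.1–36.2 | 32.7–34.5 | 35.2–35.6 |
| 40% / 55 | 84.0 | 84.0–84.1 | 79.1–82.3 | 82.6–83.2 |

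In the 25%/110 cell the chance of a futility stop under the assumed effect is 10.4–12.3% (observed rates) or 5.8–6.8% (z from Pearson or likelihood ratio). Taking the interim z from Fisher or Yates p-values goes lower, 74.7–78.1%. Every version is below 80%. The 40%/55 cell falls below 80% only with observed rates and the 13/13 split.

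**3. What the 55 column represents.** With pairs and whole-household allocation, effective N = 110/(1 + ρ), which is 55 only at ρ = 1. With participants allocated 55/55 among 55 pairs, the expected pairs are 55·(55·54)/(110·109) = 13.62 both on lambda, 13.62 both on placebo and 27.75 split.
- Let V = p₁(1−p₁) + p₂(1−p₂), and let C = p₂ − p₁p₂, the largest possible covariance in a split pair.
- Variance of the difference = V/55 + 2·13.62·V/55² − 2·27.75·C/55².
- 25%: V = 0.235, C = 0.0375. Variance 0.00570 against 0.00427 uncorrelated, so effective N = 110 × 0.00427/0.00570 ≈ 82.
- 40%: V = 0.2875, C = 0.03. Variance 0.00727 against 0.00523, so effective N ≈ 79.

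These need exactly two members per household. With assumed mixes of 1–3 or 1–4 members averaging two, the bound is 69–78. In each case it exceeds 55.

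**4. The planned type of model.** For unclustered logistic regression at 25% vs 5% and 55 per arm, Wald power is 78.6% if an event-free arm counts as non-significant. Likelihood ratio power is 88.8% (86.1–86.7% with both stopping rules). The likelihood ratio test buys part of this with size: its exact type I error is 5.4, 6.0 and 8.5% at common rates of 25, 10 and 5%, against 3.0, 2.0 and 0.9% for Fisher.

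A simulation of the mixed model (2000 runs per scenario, 55 pairs, likelihood ratio, both rules) used assumed latent household correlations of 0.3 and 0.6. It gave 86.2 and 88.2% with participants randomised, but 81.1 and 73.9% with whole households randomised. Monte Carlo error is about 1.3–2 points, and without an interim the test rejected 6.2% of null runs at correlation 0.3.

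**The case against.** Nothing in the table is miscalculated; each cell is correct for the test that reproduces it. The 80% sentence claims many scenarios, not all, and 36.1% is printed beside it. The 99.6% cell supports it whatever the stopping rules, and the 84.0% cell in nearly every version. Leaving futility out of a power calculation is a common planning choice, and 14.4 does not call the rule binding. All of this stands. It limits the point to a table that does not describe the design and one cell that loses its margin.

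Three stronger readings are tempting, and the documents do not support them.
- *The trial is underpowered.* Under the planned type of model, power may be above or below the printed figure, depending on a test that 13.2.1 does not name. Equally, 88.8% cannot be called the true power: it is one choice of test, with type I error above 5%.
- *The 55 column is an error.* Section 13.1 discloses it as the low end of a bracket, for want of correlation data. It is over-conservative only if participants are randomised individually, which is how the documents read, although they never expressly exclude allocation by household. A firm floor of 79–82 is not available either: the plan says about two per household, and PCR results divide household members between Groups A and B.
- *The loss is 3–4 points.* That follows from one way of computing conditional power. Another common one gives 1.1–1.5 points.

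**Conclusion.** The point holds as a mismatch between the stated power and the planned design. The table is fixed-sample Fisher-type power, while the text names proportional odds and mixed logistic models. On the table's own test, obeying the futility stop moves the 25%/110 cell to about 76–79% and the 40%/55 cell to about 79–83%; the efficacy limits cost nothing. If futility is advisory, the loss is smaller or nil. Of the assumptions behind these ranges (half-sample look, listed splits, complete outcomes, current-trend conditional power), the largest source of spread is the method for conditional power, which 14.4 leaves open. The reproduction of the table and the direction of the futility effect are firm; the exact replacement figure is not. It is worth correcting because the remedy is cheap, and it gives no ground for changing the sample size.

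**What to change.** Recompute the 13.1 table by simulation for the 13.2.1 mixed logistic model. Use a named test whose type I error is checked at the expected rates and that handles an event-free arm, the actual unit of randomisation (stated in 8.9), a range of household correlations in place of the single 55-cluster column, and the 14.4 efficacy and futility rules. State in 14.4 how conditional power is computed and whether futility is binding. Replace the reference to proportional odds with the planned model, and restate the 80% sentence from the result.

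If the Fisher-type calculation is kept, label it as such and give the 25%/110 cell as about 76–79% with futility obeyed.

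The cost is a short simulation, one table and a few sentences, and possibly a figure 1–4 points less favourable. Enrolment does not change.

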13.2 Statistical Analysis

13.2.1 Analyses will include all randomized participants Our primary analysis for both the prevention and treatment cohorts (outcomes of non-infection and resolution, respectively) will be mixed model logistic regression correcting for within-household correlation as a random effect. In addition to the placebo cumulative infectivity and odds ratios, we will express the overall

cumulative incidence of infection and the difference between lambda interferon vs. placebo using nonlinear combination (i.e., inverse logit of the placebo and active treatment groups and the difference of these after the inverse logit transformation). Statistical inference will use a two-sided Type 1 error rate of 0.05 and 95% confidence intervals.

For the exploratory treatment cohort, we will similarly examine clearance of infection.

In addition, we will perform survival analysis for time to infection in the prevention cohort and time to infection clearance in the treatment cohort, modeling within cluster correlation of hazard as a random effect (frailty).

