Participants who are found to be infected with SARS-CoV-2 at baseline (Group B) or who become infected during the course of the study (Group A) will not return to the study site until Day 28 or until criteria for discontinuation of infected status is met per HEIC standards, whichever occurs later. In the event that an interim in-person visit is required to evaluate an adverse event, these participants may be seen in an ambulatory setting equipped for encounters with SARS-CoV-2 infected persons. In the event that participants become hospitalized, study evaluations that coincide with clinical care will be abstracted from the medical record. Research-specific evaluations will not continue in the inpatient setting.

11. Risks and Benefits

Potential Risks of Treatment

Identified risks associated with treatment with Lambda based on nonclinical and/or clinical data, as well as potential class effects, include hepatobiliary toxicity (transaminase elevations with or without hyperbilirubinemia) and injection site reactions; potential risks include neuropsychiatric disorders (including depression), cardiovascular events, immunogenicity/hypersensitivity reactions, autoimmune disorders, elevated amylase/lipase, dermatitis, hypersensitivity reaction, injection site reaction, and reproductive risk. Complete information on preclinical and clinical safety data is located in the Investigator Brochure.

Potential Benefits of Participation

Potential benefits include prevention of infection with SARS-CoV-2 infection or reduction in severity of COVID-19 symptoms. It is not yet known whether Lambda will have any benefit in this population.

Alternatives to Participation

The alternative to participation in this study is routine care and monitoring following close contact with an individual with COVID-19.

12. Outcome measures

12.1 Group A Prevention cohort primary endpoint:

- No evidence of SARS-CoV-2 infection at or before study day 28

For the purpose of the study endpoint, SARS-CoV-2 infection is defined as any of the following outcomes:

1. SARS-CoV-2 detected in upper respiratory samples at any of day 7, day 14 or day 21; or
2. New finding of serum antibodies (IgA or IgG) against the SARS-CoV-2 spike protein according to validated specifications and performance characteristics at or prior to day 28.

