13.2.3 Sensitivity analysis for missing data

We expect very low missingness of data in our results. We will explore the demographic and clinical characteristics comparing persons with full and incomplete follow-up, and try to define the mechanism of missingness with the input of study staff about clinical operations. This experiential input is necessary, because there is no data-driven mechanism to decide on non-ignorability of missing data. For Missing Completely At Random (MCAR) or Missing At Random (MAR) data mechanisms, as sensitivity analysis, we will use multiple imputation methods to test the robustness of our results.

14. Safety Oversight

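### The Group A endpoint leaves off-schedule positive PCRs and missing tests unscored, so a clinically confirmed infection can count as prevention

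*Combined protocol and SAP*

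**What the plan says.** **Endpoint.** Section 12.1, like the synopsis, makes Group A success "No evidence of SARS-CoV-2 infection at or before study day 28". Infection has two criteria. The swab criterion is "SARS-CoV-2 detected in upper respiratory samples at any of day 7, day 14 or day 21". The serology criterion, which must be met no later than day 28, is "New finding of serum antibodies (IgA or IgG) against the SARS-CoV-2 spike protein". Both are positive findings. Neither place states which negative tests must be on file before a participant counts as uninfected.

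**Analysis set and model.** Section 13.2.1 says "Analyses will include all randomized participants" and names "mixed model logistic regression correcting for within-household correlation as a random effect" as the primary analysis. It gives no rule for a missing outcome. Section 13.1 expects that "few, if any participants will not start treatment and be excluded from the primary analysis", so the two sections describe the analysis set differently.

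**Testing.**
- Sections 8.1.1 and 8.11 send Group A participants who develop symptoms to clinical testing, whenever symptoms start.
- Section 8.11 states study swabs at days 7, 14 and 28 for those without symptoms. The Section 7.2 schedule makes no such distinction. Neither has a day 21 swab.
- Section 8.12 draws serology only at entry and day 28. Section 7.2 gives the day 28 visit a window of ±4 days.
- Section 10 keeps participants who become infected off site until day 28 or infection-control clearance, whichever is later. For those in hospital, evaluations that coincide with clinical care are abstracted from the record, but "Research-specific evaluations will not continue in the inpatient setting".

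**Missing data.** Section 13.2.3 expects very little. It compares complete and incomplete follow-up and says: "For Missing Completely At Random (MCAR) or Missing At Random (MAR) data mechanisms, as sensitivity analysis, we will use multiple imputation methods". It acknowledges that data alone cannot settle whether missingness is ignorable, and names no analysis for the case where it is not.

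**The concern.** An endpoint defined as the absence of positive findings needs two further rules: which tests must be present for a negative call, and which positives count. Section 12.1 gives neither in full, so two analysts could score the same participant differently, and the choice could be made after data are seen.

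The link to infection is specific. A Group A participant develops symptoms and has a positive clinical PCR on a day other than 7, 14 or 21. The person then stays off site until clearance, which may come after day 28, or is admitted and has no further research evaluations. If the antibody sample is missing, or is drawn after day 28 (even within the visit window), neither criterion is met as written. The clinical result may be in the record, but nothing says that it counts. A known infection would then enter the primary analysis as a success.

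Equal loss of infections in both arms dilutes the effect. Greater loss in the Lambda arm creates an apparent benefit.

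**Working it through.** **Inputs.** From Section 13.1: placebo infection 25% or 40%, Lambda 5%, 110 participants at 1:1 (55 per arm), two-sided alpha 0.05. The documents give no missingness rate, so every rate below is an assumption.

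**1. The plan's own figures.** Power is the sum over all pairs (a, b) of Bin(a; n, p1) × Bin(b; n, p2), taken where the two-sided Fisher exact p is at most 0.05.

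| | n = 55 per arm | n = 27 per arm |
|---|---|---|
| 25% v 5% | 80.1% | 36.1% |
| 40% v 5% | 99.6% | 84.0% |

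All four cells match the table in Section 13.1. That table therefore assumes every outcome is observed.

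**2. A fraction f of infections unobserved in both arms and scored as success.** Each observed rate becomes p × (1 − f). At f = 20%, 25% × 0.8 = 20% and 5% × 0.8 = 4%, a difference of 16 points instead of 20.

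| f | Rates (25% v 5%) | Difference | Power | Power at 40% v 5% |
|---|---|---|---|---|
| 0 | 25.00 v 5.00 | 20 | 80.1% | 99.6% |
| 5% | 23.75 v 4.75 | 19 | 77.1% | 99.3% |
| 10% | 22.50 v 4.50 | 18 | 73.7% | 98.9% |
| 20% | 20.00 v 4.00 | 16 | 65.9% | 97.5% |

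If only placebo infections are lost, at f = 10%, the rates are 22.5% v 5% and power is 69.8%.

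**3. Comparator: the same share of all participants lost at random and treated as missing.** The difference stays at 20 points. Power at 25% v 5% is 77.2, 74.8 and 69.5% for 5, 10 and 20% loss (52, 50 and 44 per arm).

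**4. No true effect, infections unobserved in the Lambda arm only.** With 25% truly infected in both arms and a fraction q of Lambda infections scored as success, the apparent benefit is 25% × q.

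| q | Share of Lambda arm affected | Apparent benefit (points) | Chance of a significant result for Lambda |
|---|---|---|---|
| 0 | 0 | 0 | 1.5% |
| 20% | 5.0% | 5.0 | 5.9% |
| 30% | 7.5% | 7.5 | 10.7% |
| 40% | 10.0% | 10.0 | 18.4% |

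**5. Tipping point.** Expected counts are 0.25 × 55 = 13.75 and 0.05 × 55 = 2.75, taken as 14 and 3. Fisher p for 14/55 v 3/55 is 0.007. If one, two or three Lambda participants scored as successes were in fact infected, p becomes 0.019, 0.042 or 0.082. Three participants are 3/55 = 5.5% of the arm. At 40% in placebo (22 v 3), nine are needed (22 v 12, p = 0.063).

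**The case against.** A reader might infer that the plan counts every missing outcome as a success. The documents do not say so. Naming the analysis population is not a scoring rule, and Section 13.2.3 treats incomplete follow-up as something to impute, which would be pointless if those participants were already successes. A model fitted to observed outcomes is an equally open reading. That objection stands: the rule is unspecified.

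A reader might also infer that keeping infected participants off site generally hides infections. It does not. Anyone already positive on a qualifying study swab has failed, and later gaps cannot reverse that. Home kits cover sampling through day 14, the day 7 and 14 visits may be remote, day 28 serology is planned for everyone, and clinical evaluations in hospital are abstracted. Misclassification requires no qualifying positive swab and also no positive antibody result by day 28.

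The sizes are modest at low missingness and small if placebo infection is 40%. Most of the power loss comes from losing data at all: at 10%, scoring as success gives 73.7% and random loss treated as missing gives 74.8%.

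These points narrow the concern but do not remove it. No text counts an off-schedule or abstracted PCR toward the endpoint, serology after entry is a single draw, and nothing covers non-ignorable missingness.

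**Conclusion.** The concern holds as a gap in the endpoint definition and missing-data rules. Followed as written, criterion 1 ignores a positive clinical PCR on another day, names a day 21 swab that is not scheduled, and omits the day 28 swab in Section 8.11. Success requires no valid negative test. The only remedy for missing outcomes is imputation under MCAR or MAR, as a sensitivity analysis.

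If 5 to 20% of infections were unobserved in both arms and scored as success, power would be 77.1 to 65.9% instead of 80.1% at 25% v 5%, and 99.3 to 97.5% at 40% v 5%. Equal loss dilutes the effect; a false benefit needs loss that differs by arm, and the documents give no evidence of that. Section 9.4 states blinding for participants only, so it cannot be excluded by design. Because three Lambda participants can reverse the expected result at 25% v 5%, an expectation of very low missingness is not enough protection.

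These figures use Fisher's exact test with independent participants, which reproduces the plan's table, and not the planned mixed model.

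**What to change.** 1. In the synopsis and Section 12.1, count as infection any positive study or clinical PCR, including abstracted results, or new antibodies, through the day 28 visit window. Reconcile the day 21 and day 28 swabs across Sections 7.2, 8.11 and 12.1.
2. Score success only when a pre-stated minimum of evaluable negative tests is present. Otherwise the outcome is missing, not a success.
3. In Section 13.2, state the primary handling of missing outcomes and reconcile the analysis set with Section 13.1. If multiple imputation is used, include arm, household, observed swab results, Day 0 serology and symptoms.
4. In Section 13.2.3, add a tipping-point analysis that varies the infection rate among participants with missing outcomes separately by arm.

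The cost is changed wording and some extra analysis, with slightly wider intervals when outcomes are missing. Apart from whatever the swab reconciliation settles, no new visits or participants are needed.
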